9.4.2 Safety Analyses

All safety analyses (Table 10) will be performed on the full analysis set (FAS). Should any subjects receive a treatment other than their randomized treatment, the treatment as received will be used in the safety presentation.

Table 10 Safety Analysis

Endpoint	Statistical Analysis Methods
TEAEs, including abuse-related AEs and AEs related to MHIs	TEAEs will be coded according to MedDRA and summarized by treatment group, system organ class, and preferred term. Additional summaries by seriousness, severity, relationship to IMP, and dose at the time of onset will also be prepared.
Other safety	The C-SSRS, ESS, QUIP-RS, laboratory data, vital sign data, and ECG data will be summarized with descriptive statistics.

Abbreviations: AE = adverse events, C-SSRS = Columbia-Suicide Severity Rating Scale, ECG = electrocardiogram, ESS = Epworth Sleepiness Scale, IMP = investigational medicinal product, MedDRA = Medical Dictionary for Regulatory Activities, MHIs = medication handling irregularities, QUIP-RS = Questionnaire for Impulsive-Compulsive Disorders – Rating Scale, TEAE = treatment-emergent adverse event.

9.4.3 Other Analyses

Plasma concentrations of tavapadon and its major metabolite (if required) will be summarized by dose, visit, and nominal time (if applicable). All PK exposure-response analyses will be described in a separate PK analysis plan that will be finalized before database lock.

Plasma concentrations will also be pooled with data from other trials in a population PK analysis to describe the time course of plasma concentrations of tavapadon and the influence of covariates (eg, body weight, age, sex, race, concomitant medications) on PK

parameters. The results of population PK analysis and response-exposure analyses will be presented separately from the main clinical study report (CSR).

9.4.4 Concentration-QT Analysis

The effect of tavapadon on the QT interval will be evaluated in a US-specific substudy, as described in [Section 10.7](#) (Appendix 7). The results of the C-QT analysis will be presented separately from the main CSR.

10 SUPPORTING DOCUMENTATION AND OPERATIONAL CONSIDERATIONS

10.1 Appendix 1: Regulatory, Ethical, and Trial Oversight Considerations

10.1.1 Regulatory and Ethical Considerations

This trial will be conducted in accordance with the protocol and with the following:

- Consensus ethical principles derived from international guidelines including the Declaration of Helsinki and Council for International Organizations of Medical Sciences (CIOMS) International Ethical Guidelines
- Applicable International Conference on Harmonisation (ICH) GCP Guidelines
- Applicable laws and regulations

The protocol, protocol amendments, ICF, Investigator Brochure, and other relevant documents (eg, advertisements) must be submitted to an IRB/IEC by the investigator and reviewed and approved by the IRB/IEC before the trial is initiated. Any amendments to the protocol will require IRB/IEC approval before implementation of changes made to the trial design, except for changes necessary to eliminate an immediate hazard to trial subjects.

The investigator will be responsible for the following:

- Providing written summaries of the status of the trial to the IRB/IEC annually or more frequently in accordance with the requirements, policies, and procedures established by the IRB/IEC
- Notifying the IRB/IEC of SAEs/AESI or other significant safety findings as required by IRB/IEC procedures
- Providing oversight of the conduct of the trial at the site and adherence to requirements of 21 Code of Federal Regulations (CFR), ICH guidelines, the IRB/IEC, European regulation 536/2014 for clinical trials (if applicable), and all other applicable local regulations

10.1.2 *Financial Disclosure*

Investigators and sub-investigators will provide the sponsor with sufficient, accurate financial information as requested to allow the sponsor to submit complete and accurate financial certification or disclosure statements to the appropriate regulatory authorities. Investigators are responsible for providing information on financial interests during the course of the trial and for 1 year after completion of the trial.

10.1.3 *Informed Consent Process*

The investigator or his/her representative will explain the nature of the trial to the subject or his/her legally authorized representative (as defined per local regulations) and answer all questions regarding the trial.

Subjects must be informed that their participation is voluntary. Subjects or their legally authorized representative as, applicable by local law, will be required to sign a statement of informed consent (either electronic or written) that meets the requirements of 21 CFR 50, local regulations, ICH guidelines, Health Insurance Portability and Accountability Act (HIPAA) requirements, where applicable, and the IRB/IEC or trial center.

The medical record must include a statement that informed consent was obtained before the subject was enrolled in the trial and the date consent was obtained. The authorized person obtaining the informed consent must also sign the ICF.

Subjects must be re-consented to the most current version of the ICF(s) during their participation in the trial. A copy of the ICF(s) must be provided to the subject or the subject's legally authorized representative (as defined per local regulations).

A separate and similar consent process will be followed for the optional banked biospecimen research samples. The investigator or authorized designee will explain the objectives of the exploratory research to each subject. Subjects will be told that they are free to refuse to participate and may withdraw their consent at any time and for any reason during the storage period. A separate signature will be required to document subject agreement to allow specimens to be used for exploratory research. Subjects who decline to participate in this optional research will not provide this separate signature.

10.1.4 *Data Protection*

Subjects will be assigned a unique identifier by the sponsor. Any subject records or datasets that are transferred to the sponsor will contain the identifier only; subject names or any information which would make the subject identifiable will not be transferred.

The subject must be informed that his/her personal trial-related data will be used by the sponsor in accordance with local data protection law. The level of disclosure must also be explained to the subject.

The subject must be informed that his/her medical records may be examined by Clinical Quality Assurance auditors or other authorized personnel appointed by the sponsor, by appropriate IRB/IEC members, and by inspectors from regulatory authorities.

10.1.5 Dissemination of Clinical Trial Data

Cerevel fulfills its commitment to publicly disclose clinical trial results through posting trial results on ClinicalTrials.gov, the European Clinical Trials Database (EudraCT), and other public registries in accordance with applicable local laws/regulations.

In all cases, trial results are reported by Cerevel in an objective, accurate, balanced, and complete manner and are reported regardless of trial outcome or the country in which the trial was conducted.

US Basic Results are posted on Clinicaltrials.gov for all Cerevel-sponsored interventional trials that are conducted in subjects and that evaluate the safety and/or efficacy of a Cerevel product, regardless of the geographical location in which the trial is conducted. US Basic Results are submitted for posting within 1 year of the primary completion date, as defined in [Section 4.4](#), for trials in adult populations or within 6 months of the primary completion date for trials in pediatric populations.

Cerevel posts European Union (EU) Basic Results on EudraCT for all Cerevel-sponsored interventional trials that are in scope of EU requirements. EU Basic Results are submitted for posting within 1 year of the primary completion date as defined in [Section 4.4](#), for trials in adult populations or within 6 months of the primary completion date for trials in pediatric populations.

10.1.6 Data Quality Assurance

All subject data relating to the trial will be recorded on printed or eCRFs unless transmitted to the sponsor or designee electronically (eg, laboratory data). The investigator is responsible for verifying that data entries are accurate and correct by physically or electronically signing the eCRF.

The investigator must maintain accurate documentation (source data) that supports the information entered in the eCRF.

The investigator must permit trial-related monitoring, audits, IRB/IEC review, and regulatory agency inspections and provide direct access to source data documents.

Monitoring details describing strategy (eg, risk-based initiatives in operations and quality such as Risk Management and Mitigation Strategies and Analytical Risk-Based Monitoring), methods, responsibilities, and requirements, including handling of noncompliance issues and monitoring techniques (central, remote, or on-site monitoring) are provided in the Clinical Monitoring Plan.

The sponsor or designee is responsible for the data management of this trial including quality checking of the data.

The sponsor assumes accountability for actions delegated to other individuals (eg, Contract Research Organizations).

Trial monitors will perform ongoing source data verification to confirm that data entered onto the eCRF by authorized site personnel are accurate, complete, and verifiable from source documents; that the safety and rights of subjects are being protected; and that the trial is being conducted in accordance with the currently approved protocol and any other trial agreements, ICH GCP, and all applicable regulatory requirements.

Records and documents, including signed ICFs, pertaining to the conduct of this trial must be retained by the investigator for the longest of the following periods:

- At least 2 years after the date on which approval to market the drug is obtained (or if development of the IMP is discontinued, the date regulatory authorities were notified of discontinuation)
- At least 3 years after the sponsor has notified the investigator that the final report has been filed with regulatory authorities
- A longer period if required by local regulations or institutional policies

No records may be destroyed during the retention period without the written approval of the sponsor. No records may be transferred to another location or party without written notification to the sponsor.

10.1.7 Source Documents

Source documents provide evidence for the existence of the subject and substantiate the integrity of the data collected. Source documents are filed at the investigator's site.

Data entered in the eCRF that are transcribed from source documents must be consistent with the source documents or the discrepancies must be explained. The investigator may need to request previous medical records or transfer records, depending on the trial. Also, current medical records must be available.

Definitions of what constitutes source data are included in the Clinical Monitoring Plan.

10.1.8 Trial and Site Closure

The sponsor designee reserves the right to close the trial site or terminate the trial at any time for any reason at the sole discretion of the sponsor. Trial sites will be closed upon trial completion. A trial site is considered closed when all required documents and trial supplies have been collected and a trial-site closure visit has been performed.

The investigator may initiate trial-site closure at any time, provided there is reasonable cause and sufficient notice is given in advance of the intended termination.

Reasons for the early closure of a trial site by the sponsor or investigator may include but are not limited to:

- Failure of the investigator to comply with the protocol, the requirements of the IRB/IEC or local health authorities, the sponsor's procedures, or GCP guidelines
- Inadequate recruitment of subjects by the investigator
- Discontinuation of further trial intervention development

10.1.9 *Publication Policy*

The results of this trial may be published or presented at scientific meetings. If this is foreseen, the investigator agrees to submit all manuscripts or abstracts to the sponsor before submission. This allows the sponsor to protect proprietary information and to provide comments.

The sponsor will comply with the requirements for publication of trial results. In accordance with standard editorial and ethical practice, the sponsor will generally support publication of multicenter trials only in their entirety and not as individual site data. In this case, a coordinating investigator will be designated by mutual agreement.

Authorship will be determined by mutual agreement and in line with International Committee of Medical Journal Editors authorship requirements.

10.2 Appendix 2: Clinical Laboratory Tests

The tests detailed in [Table 11](#) will be performed at the time points designated in the Schedule of Assessments ([Table 2](#)). Additional tests may be performed at any time during the trial as determined necessary by the investigator or required by local regulations.

Table 11 Protocol-Required Safety Laboratory Assessments

Laboratory Assessments	Parameters		
Hematology	Platelet count RBC count Hemoglobin Hematocrit MCV	WBC count with differential: Neutrophils Lymphocytes Monocytes Eosinophils Basophils	
Chemistry	BUN Creatinine Albumin Cholesterol Total HDL-C LDL-C Triglycerides	Potassium Sodium Calcium Bicarbonate Chloride Magnesium Glucose	ALT AST Alkaline phosphatase GGT CPK Total bilirubin Direct bilirubin Total protein TSH (with reflex-free T3/T4 if abnormal)
Urinalysis	Specific gravity Color	Dipstick ^a pH Glucose Protein Blood Ketones Bilirubin Urobilinogen Nitrite Leukocyte esterase	
Additional Tests	Prolactin (results will not be reported to investigative sites or other blinded personnel until the trial is unblinded). Serum pregnancy test (at screening and as needed for WOCBP). Urine dipstick pregnancy test (at all other time points as needed for WOCBP), followed by serum pregnancy test if urine dipstick test is positive. If serum CPK value is $>3 \times$ ULN, CPK reflex for isoenzymes. If serum CPK value is $>5 \times$ ULN, serum and urine myoglobin.		

Table 11 Protocol-Required Safety Laboratory Assessments

Laboratory Assessments	Parameters
Screening Tests	Urine drug screen for illicit drugs Serology (HIV, HbsAg, and HCV)

Abbreviations: AE = adverse event, ALT = alanine aminotransferase, AST = aspartate aminotransferase, BUN = blood urea nitrogen, CPK = creatine phosphokinase, eCRF = electronic case report from, GGT = gamma-glutamyl transferase, HbsAg = hepatitis B surface antigen, HCV = hepatitis C virus, HDL-C = high-density lipoprotein cholesterol, HIV = human immunodeficiency virus, LDL-C = low-density lipoprotein cholesterol, MCV = mean corpuscular volume, RBC = red blood cell, T3 = triiodothyronine, T4 = thyroxine, TSH = thyroid-stimulating hormone, ULN = upper limit of normal, WBC = white blood cell, WOCBP = women of childbearing potential.

- a. Results of the dipstick urine analysis will not be recorded on the eCRFs. Any clinically significant finding will be captured as an AE.

Investigators must document their review of each laboratory safety report and file the laboratory report as appropriate. Any clinically significant laboratory abnormality must be reported as an AE.

10.3 Appendix 3: Adverse Events: Definitions and Procedures for Recording, Evaluating, Follow-up, and Reporting

10.3.1 Definition of AE

Table 12 Definition of AE

AE Definition

• An AE is any untoward medical occurrence in a patient or clinical trial subject, temporally associated with the use of trial intervention, whether or not considered related to the trial intervention.• NOTE: Signs and symptoms and/or abnormal laboratory test result indicating a common underlying pathology/diagnosis should be reported as a single AE.

Abbreviation: AE = adverse event.

Table 13 Events Meeting the AE Definition

Events Meeting the AE Definition

• Any abnormal laboratory test results (hematology, clinical chemistry, or urinalysis) or other safety assessments (eg, ECG, radiological scans, vital signs measurements), including those that worsen from baseline, considered clinically significant in the medical and scientific judgment of the investigator.• Exacerbation of a chronic or intermittent pre-existing condition including either an increase in frequency and/or intensity of the condition.• New conditions detected or diagnosed after trial intervention administration even though it may have been present before the start of the trial.• Signs, symptoms, or the clinical manifestations of a suspected drug-drug interaction.• Signs, symptoms, or the clinical manifestations of a suspected overdose of either trial intervention or a concomitant medication. “Lack of efficacy” or “failure of expected pharmacological action” per se will not be reported as an AE or SAE/AESI. Such instances will be captured in the efficacy assessments.

Abbreviations: AE = adverse event, AESI = adverse event of special interest, ECG = electrocardiogram, SAE = serious adverse event.

10.3.2 Definition of SAE

If an event is not an AE per definition above, then it cannot be an SAE even if serious conditions are met (eg, hospitalization for signs/symptoms of the disease under trial, death due to progression of disease).

Table 14 Definition of SAE

An SAE is defined as any untoward medical occurrence that, at any dose in the view of either the investigator or sponsor, results in any of the following outcome:

a. Results in death

b. Is life-threatening

The term 'life-threatening' in the definition of 'serious' refers to an event in which the subject was at risk of death at the time of the event. It does not refer to an event, which hypothetically might have caused death, if it were more severe.

c. Requires inpatient hospitalization or prolongation of existing hospitalization

In general, hospitalization signifies that the subject has been detained (usually involving at least an overnight stay) at the hospital or emergency ward for observation and/or treatment that would not have been appropriate in the physician's office or outpatient setting. Complications that occur during hospitalization are AEs. If a complication prolongs hospitalization or fulfills any other serious criteria, the event is serious. When in doubt as to whether "hospitalization" occurred or was necessary, the AE should be considered serious.

Hospitalization for elective treatment of a pre-existing condition that did not worsen from baseline is not considered an AE.

d. Results in persistent disability/incapacity

The term disability means a substantial disruption of a person's ability to conduct normal life functions.

This definition is not intended to include experiences of relatively minor medical significance such as uncomplicated headache, nausea, vomiting, diarrhea, influenza, and accidental trauma (eg, sprained ankle) which may interfere with or prevent everyday life functions but do not constitute a substantial disruption.

e. Is a congenital anomaly/birth defect

f. Other situations:

Medical or scientific judgment should be exercised in deciding whether SAE reporting is appropriate in other situations such as important medical events that may not be immediately life-threatening or result in death or hospitalization but may jeopardize the subject or may require medical or surgical intervention to prevent one of the other outcomes listed in the above definition. These events should usually be considered serious.

Examples of such events include invasive or malignant cancers, intensive treatment in an emergency room or at home for allergic bronchospasm, or blood dyscrasias.

Abbreviations: AE = adverse event, SAE = serious adverse event.

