The safety results across all clinical trials demonstrate that tavapadon was generally well tolerated up to a titrated dose of 15 mg QD in subjects with PD, either as monotherapy (early PD) or as adjunctive treatment with a stable dose of L-Dopa (advanced PD). A dose-dependent increase in the frequencies of nausea and headache was observed across all trials. Nausea, vomiting, dyskinesia, fall, fatigue, sleep disorder, and tremors were the most common AEs leading to discontinuation of tavapadon. The appearance of nausea, orthostatic blood pressure changes, and fatigue is often related to the speed of titration with dopamine receptor agonists (historically with D2 agents) and may be mitigated by a slower titration method.

No notable differences in laboratory abnormalities, electrocardiogram (ECG) parameters, or suicidality assessments were observed between tavapadon and placebo. Multidose cohorts in Phase 1 trials in healthy volunteers and subjects with PD (including subjects with PD who were treated at doses of up to 25 mg QD of tavapadon) did not suggest that tavapadon prolonged the QT interval corrected for heart rate by Fridericia's formula (QTcF). Trials of longer treatment duration suggest a tavapadon dose-related decrease from baseline in systolic and/or diastolic parameters, with some cases of asymptomatic hypotension. This finding is common with dopamine D2 agonists and is prevalent in the population of patients with PD whether treatment naïve or treated with L-Dopa.

Taken together, the current data suggest an appropriate benefit-risk ratio for further evaluation of tavapadon in Phase 3 clinical trials at doses up to 15 mg QD. Additional information about the known and expected benefits, risks, and AEs of tavapadon is provided in the Investigator's Brochure.

In response to the COVID-19 pandemic, Cerevel has performed a risk assessment of this trial and the investigator of each individual trial site and has implemented measures throughout the protocol, which prioritizes trial participant safety and data validity.

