5.9.3.4. Impact of Missing Values Handling

Whilst every effort will be made to prevent avoidable missing values during the study conduct ([National Research Council, 2010](#)), it is unrealistic to expect no missing values in clinical trials. The impact of missing values on the analysis results will be assessed by the sensitivity analyses described below.

Under Missing at Random (MAR) Assumption

Multiple imputation (MI) will be performed to replace each missing value with a set of plausible values that represent the uncertainty about the correct value to impute. The Markov chain (MCMC) method will be utilized for the mITT set. SAS PROC MI will be used to generate 27 possible imputed datasets: Each of these datasets will be analyzed using PROC MIXED in SAS using the MMRM model as described in [Section 5.9.2](#). The results of the analyses of the datasets will be combined using PROC MIANALYZE to produce an inferential result.

Considerations of Data Potentially Missing Not at Random (MNAR)

A pattern mixture model (PMM) approach will be used to address potentially MNAR patterns. The following three patterns of subjects in the mITT set will be considered:

- 1) Subjects with no missing values from discontinuation or from initiation of prohibited Parkinson's disease concomitant mediation during treatment period.
- 2) Subjects with missing values from the types of ICEs below will be considered having MNAR
 - a. Subjects who discontinue due to reasons, as recorded on the eCRF, of lack of efficacy, adverse events associated with motor symptoms of Parkinson's disease, physician decision, and withdrawal by subject.
 - b. Subjects who initiated concomitant Parkinson's disease medications (ATC classifications of ADAMANTANE DERIVATIVES, DOPAMINE AGONISTS, MONOAMINE OXIDASE B INHIBITORS, OTHER ANTI-PARKINSON DRUGS, OTHER DOPAMINERGIC AGENTS, or DOPA AND DOPA DERIVATIVES) after the first dose of IMP and prior to the last dose of IMP with a use duration of 7 days or more will be considered having a potential confounding ICE. The efficacy data post ICE will be treated as missing with the missing pattern of MNAR.

The MNAR cases will be identified and documented prior to database lock and unblinding ([Section 9.5](#)).

- 3) Subjects with missing values from the type of ICEs below will be considered as having MAR

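### The examples in Protocol 10.3.2 treat PD-related hospitalization and death from progression as non-AEs, but the definitions they rely on contain no such exclusion, so sites can classify the same serious event differently

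*Protocol*

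**What the plan says.** The rule is one conditional sentence in Protocol 10.3.2: "If an event is not an AE per definition above, then it cannot be an SAE even if serious conditions are met". Its consequence runs straight into the first example, "it cannot be an SAE even if serious conditions are met (eg, hospitalization for signs/symptoms of the disease under trial", and the parenthesis gives two examples in all: "hospitalization for signs/symptoms of the disease under trial, death due to progression of disease".

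The definitions it points back to are in Protocol 10.3.1:

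- Table 12: "An AE is any untoward medical occurrence in a patient or clinical trial subject, temporally associated with the use of trial intervention", related or not.
- Table 13 lists among AEs: "Exacerbation of a chronic or intermittent pre-existing condition including either an increase in frequency and/or intensity of the condition". It also lists conditions first found after treatment began, and vital-sign changes that the investigator judges clinically significant.
- Table 13 has one efficacy-type exclusion. Lack of efficacy "per se will not be reported as an AE or SAE/AESI. Such instances will be captured in the efficacy assessments".

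Table 14 then gives the seriousness criteria, which either the investigator or the sponsor may judge to be met. They include death and inpatient admission. Its only carve-out for admissions is elective treatment of a pre-existing condition that had not worsened.

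**The concern.** A site deciding whether to report an admission is likely to read the examples as the sponsor's instruction, and they name Parkinson's disease (PD) admissions and PD deaths as events outside AE reporting. A site that goes by Tables 12 to 14 reaches the opposite answer for the same patient.

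The overlap between disease and possible drug effect is documented. Protocol 2.3 reports from earlier trials that "Nausea, vomiting, dyskinesia, fall, fatigue, sleep disorder, and tremors were the most common AEs leading to discontinuation of tavapadon". Falls, tremor and sleep disorder can each be read as PD or as a reaction to treatment. Calling an event disease comes before every safety step. A drug effect put down to PD at that point never reaches the causality assessment meant to tell the two apart.

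**Working it through.** No arithmetic applies. The plan states no figure on this point, so the check is a comparison of texts.

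1. **Is the exclusion in the definitions?** Table 12 has no exception for PD. Table 13 has none either, and PD is a chronic condition present before treatment. The Table 14 carve-out needs both an elective admission and no worsening. So neither example in 10.3.2 follows from the definitions it cites.

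2. **What does the sentence do when read whole?** It applies only to an event that is not an AE. A worsening of PD that Table 13 makes an AE, and that leads to an unplanned admission, does not meet that condition. The sentence then excludes nothing, and the event is an SAE under Table 14. The same holds for a death from an event that is an AE. Strict logic therefore favours reporting, but only if the site sets the examples aside.

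3. **Do other passages settle it?** They point both ways. Protocol 7.3 lists PD worsening that calls for additional anti-PD medication as a reason for stopping separate from an adverse event. SAP 5.9.3.4 expects some discontinuations for "adverse events associated with motor symptoms of" PD, which treats such events as AEs. Protocol 8.3.4 asks that a condition found at the posttreatment examination but absent at baseline be documented as an AE.

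4. **What follows for one event?** Take an unplanned admission for worsened PD.

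| Step | Site follows the 10.3.2 example | Site follows Tables 12 to 14 |
|---|---|---|
| AE (10.3.1) | No | Yes, as an exacerbation |
| SAE (Table 14) | No | Yes, inpatient admission |
| Report within 24 hours (8.4.1) | None | Required |
| Causality assessment (Table 15) | None | Required |
| AESI if treatment stops because of it (8.4.6.3) | No, because no AE exists | Yes |
| TEAE and TESAE tables (SAP 3.2.3.2, 5.14.1) | Absent | Counted |

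5. **How many events?** A count would need an SAE rate, the share that is PD-related, and the share of sites that follow the examples. The documents give none of these.

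**The case against.** The strongest reply is that the opening condition disposes of the matter: 10.3.2 removes nothing that Tables 12 and 13 make an AE. That is correct. A reader who sees only the second half of the sentence might infer a flat rule that a PD admission can never be an SAE, and the documents do not support that. What remains is that the examples tell sites the contrary. It can also be said that the examples merely illustrate the lack-of-efficacy exclusion. The text does not tie them to it, and that exclusion is limited to lack of efficacy as such.

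A reader might also infer that admissions for syncope or hallucinations would be lost. That is unlikely in general. Hallucinations within 12 months (exclusion 7) and clinically significant orthostatic hypotension (exclusion 22) keep patients out, so on-treatment cases would usually be new and fall under Table 13's rule for new conditions.

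A further inference, that the lost events are those most likely to separate drug from placebo, has no support. The discontinuation list in Protocol 2.3 draws on earlier trials that included advanced, L-Dopa-treated PD. It shows that the event types overlap, not that events go missing in early PD. Hypotension and hallucinations are described as effects of other dopamine agonists that tavapadon aims to minimize, although 2.3 does report dose-related falls in blood pressure with some asymptomatic hypotension.

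There are partial safeguards. Any AE that leads to discontinuation is an AESI with 24-hour reporting, the sponsor may assign seriousness, and reasons for stopping are tabulated by arm (SAP 5.6, 5.8). The AESI rule works only once an event has been called an AE. A disposition table shows that a patient stopped, not that the patient was hospitalized.

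**Conclusion.** The inconsistency is real and should be corrected. It is an ambiguity created by two examples, not an outright exclusion of PD-related SAEs. Loss of events is a risk that depends on how each site reads the text.

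Its size cannot be estimated. Multiplying the 522 planned subjects by an assumed SAE rate and an assumed PD-like share would give a number, but both inputs would be invented. The result would also treat every PD-like SAE as exposed, which step 2 of the working shows to be wrong.

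The conclusion rests on one assumption: that at least some sites take the examples as guidance. If every site applied the opening condition strictly, nothing would be lost.

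**What to change.** Remove or qualify the parenthesis in 10.3.2 so that it agrees with Tables 12 to 14: an event that is an AE under Tables 12 and 13 and meets a Table 14 criterion is an SAE. Keep the lack-of-efficacy exclusion for change measured by the efficacy scales. Do not go further and declare every worsened PD sign an AE. That would turn ordinary progression, already captured by the MDS-UPDRS, into AEs and blur the exclusion.

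SAP 5.5 describes randomization-stratum errors as having already happened, so a protocol edit or site letter may come late. The check before database lock is therefore the more useful half. Compare all deaths and all discontinuations for PD worsening with the SAE database, including those recorded as lack of efficacy, a reason SAP 5.9.3.4 lists. Send the site a query about any associated hospitalization. The query is needed because the documents describe no hospitalization dataset separate from AE recording, so an admission never entered as an AE may have nothing to be reconciled against. For the same reason, the check will not find an admission classed as disease in a patient who stayed on treatment.

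The cost is one sentence or site letter, one query listing and a few more SAE reports.
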